20. STUDY SUSPENSION/TERMINATION

If for any reason the principle investigator chooses to suspend or terminate the study, the IRB shall be informed of the decision and the basis of the decision.

21. STUDY MATERIALS

The Investigator is responsible for assuring that routine medical supplies, equipment, personnel, and facilities are available to successfully implement this study plan in a timely and efficient manner. Provisions should be made for research and medical staff to sufficiently accomplish:

- Screening of subjects to identify suitable study subjects,
- Conducting and obtaining informed consent,
- Scheduling for examinations and procedures,
- Coordination, monitoring, and source data verification,
- Case Report Forms,
- Investigational devices and
- Clinical study Plan and supporting study documentation.

22. PROVISION AND INVENTORY OF STUDY DEVICES

The device and required materials will be provided to the Investigator by Alesi Surgical Ltd.

23. DATA COLLECTION AND MANAGEMENT

The investigator and study team members as delegated are responsible for collecting the data from the study. Copies of all imaging documentation files will be collected and retained by the study team.

Case Report Forms (CRF) specifically created for this study will be used to collect all data. Case Report Forms shall reflect the contents of this study plan. The CRF and any amendment to it shall bear a version number and each page shall be identifiable by the number and identification of the subject whose data the CRF pertains. If/when it is necessary to amend the CRFs, the Investigator shall review the study protocol to determine if an amendment to this study protocol is necessary. All study protocol amendments require IRB notification. If the amendments are significant changes in the study design IRB review and approval may be required. The Investigator will work with the IRB for all changes to ensure the proper process for implementation of change occurs.

Manually entered information on any paper study documents must be legibly written in black ink only. If changes are required, a single line must be drawn through the incorrect information, the correct information written in, and the changes initialed and dated. The reason for the correction should be noted, unless obvious.

Use of white-out, obscuring incorrect data (scribbling-out), and additional comments written on the documents is prohibited.

The investigator must review sign and date each CRF or document review on a CRF review log; these responsibilities cannot be delegated to another person. The investigator is responsible for the accuracy and completeness of all study data.

All original imaging, laboratory, and procedural reports, etc., are considered source documents and will also be retained at the investigational site.

Study subjects will be identified by unique study identification numbers. The identification number is the 3-digit study number. A master key will contain the study identification number and patient identifier (as defined by the Study number, the patient ID number and the patient's initials). The master key will be stored in the study binder and kept in a secure, locked location in the Principal Investigator's office.

Study binders containing study data (including subject pain diaries) will be collected and stored in a secure, locked location in the Principal Investigator's office. Access to the records will be limited to the Lead Study Coordinator and the Principal Investigator only.

For analysis data may be extracted from case report forms and entered into Excel spreadsheets by a member of the study team. The spreadsheet(s) containing the study data set will not contain protected health information. Subjects will be identified by the 3-digit study number only (no initials). The study data set will be stored on a study team member's password-protected Mercy computer on a secure Mercy server.

Study data will not be removed from the site listed above at any time during the course of this study. Data extracted into spreadsheets may be shared outside of the facility for data analysis purposes. All shared data will be de-identified.

All public reporting of the results of this study will eliminate identifiable references to the subjects.

24. IMAGING DIAGNOSTICS

Any imaging performed for patients is considered consistent with standard of care.

25. DATA ANALYSIS PLAN

25.1. SAMPLE SIZE JUSTIFICATION

Ultravision is already cleared by the FDA for use in laparoscopic endometriosis. This post-market study is intended to evaluate user satisfaction and the relative impact the Ultravision™ System has on the procedure as opposed to demonstrating safety and efficacy. The sample size selected (20) is considered to be a sufficient quantity to establish whether or not low impact surgery is facilitated with the use of the

Ultravision™ System. This is designed as a single arm study to demonstrate feasibility of device use under low impact laparoscopy. The Ultravision will either enable the procedure to be completed as planned or not, therefore a control arm is not considered necessary to make this determination. In addition, incorporating a control arm using the same conditions without the use of Ultravision may not be in the best interest of the patient. The study design is considered to appropriate for the research question that is being posed.

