The ability to operate under “low impact” laparoscopic conditions has been shown by others to improve clinical outcomes by, for example, reducing post-surgical pain and with smaller incision sizes, improved cosmesis. For the purposes of this study “low impact” is defined as (1) a target pneumoperitoneal pressure of 10mm Hg; and (2) instead of 10mm and/or 12mm ports, the use of 3mm ports and one 5mm port. Using a standard insufflator, the combination of lower pneumoperitoneal pressure and smaller size ports creates visualization challenges for the surgeon due to the difficulty of preventing the buildup of surgical smoke within the abdomen. “Venting” or actively extracting the smoke through a trocar is known to be largely ineffective due to the narrow internal diameter of 3mm trocars, certainly unless the instrument is removed beforehand, which creates additional surgical challenges. Furthermore, operating under lower pressure can cause pneumoperitoneum to be lost upon venting of the smoke. The research question that is posed in this study is whether the Ultravision™ System, due to its unique mode of action which (unlike other smoke management approaches) provides smoke management without needing to extract or exchange CO₂, provides effective visual field clearing, thereby facilitating low impact laparoscopic surgery when using a conventional insufflator. In addition, Ultravision™ does not require CO₂ removal and replacement to achieve its intended use, thereby minimizing to the greatest extent possible patient CO₂ exposure. CO₂ is dry (effectively 0% relative humidity) and cold (typically 65F) and exposure is linked to postoperative pain and other adverse consequences such as patient cooling and tissue desiccation. Due its mode of action, Ultravision™ minimizes CO₂ exposure to the patient.

Laparoscopic surgery for the treatment of endometriosis is a common procedure for the removal of mild to moderate endometriosis. Diathermy is commonly used to remove the lesions which can be extensive, therefore this procedure presents an appropriate surgical procedure for this study.

Assessments in terms of surgical field visualization, CO₂ consumption, end tidal CO₂, patient satisfaction for cosmesis, and postoperative pain will be conducted in order to determine if the Ultravision™ System is effective in enabling laparoscopic surgery under low impact laparoscopic conditions. Adverse event information will be reported. The study is an open label single arm study.

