Study Purpose

There are five main study objectives:

1. Demonstrate the feasibility of undertaking low impact laparoscopic surgery for endometriosis when using the Ultravision™ System.
2. Assess the impact of Ultravision on visual field clarity.
3. Determine the ability to complete the procedure while maintaining an abdominal pressure of \leq 10mmHg.
4. Quantify the consumption of CO₂.
5. Collect data on additional clinical outcomes associated with the use of Ultravision and low impact surgery (i.e. end tidal CO₂ levels (EtCO₂), adverse events, cosmesis outcome, postoperative pain levels and pain medications).

Study Hypothesis

The primary hypothesis being tested in this study is that Ultravision facilitates the utilization of low impact laparoscopic surgery techniques whilst maintaining an adequate visual field throughout the procedure with low demand for CO₂ replenishment to maintain pneumoperitoneal pressure.

Study Population

The study will enroll patients indicated for laparoscopic surgery to treat endometriosis. Patients must meet all inclusion/exclusion criteria.

Study Design

This is a prospective single arm study. The study will enroll 20 patients. Comparisons to prior clinical trials and published literature will be made to assess the relative significance of the study results.

Study Endpoints

Success will be based on demonstration that the procedures using the Ultravision™ System achieves the following endpoints :

1. The ability to complete the procedure without increasing pneumoperitoneum due to visualization.
Any increase beyond 10mm Hg and the reason for change will be recorded.
2. The quality of visualization in the laparoscopic field of view will be assessed by the investigator using a Visual Analog Scale (VAS).
3. Patient satisfaction with cosmesis outcome at the discharge follow-up visit assessed by means of a survey scaled from “very unsatisfied” to “very satisfied.”
4. Post-Surgery Pain assessment based upon a Numerical Rating Scale (NRS) where 0 is “no pain at all” to 10 “worst pain imaginable” and the location of the pain using a body diagram.
5. Pain medication utilization

Other Data Collection

- End tidal CO₂ volume (etCO₂) (taken at the start of the procedure and at the completion of the procedure),
- Adverse Events,
- Electrosurgical instrument(s) used,
- Preoperative assessment: patient demographics, medical history, medication information, height and weight, pain (at intake visit)

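### Section 25.1 treats completion with Ultravision in use as showing that Ultravision enabled it; one arm of 20 can show feasibility with the device in use, not attribution to it

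*Protocol*

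**What the plan says.** Section 25.1 gives two reasons for having no control. The first is logical: Ultravision "will either enable the procedure to be completed as planned or not, therefore a control arm is not considered necessary to make this determination". The second is that a control under the same conditions without the device might not serve the patient. The section calls 20 patients "considered to be a sufficient quantity to establish whether or not low impact surgery is facilitated with the use of the" system, and says the study evaluates "user satisfaction and the relative impact the Ultravision™ System has on the procedure as opposed to demonstrating safety and efficacy". It also states a narrower aim: "This is designed as a single arm study to demonstrate feasibility of device use under low impact laparoscopy". Objective 1 in the Study Summary is likewise a feasibility objective.

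The attributing language recurs elsewhere. The primary hypothesis reads "Ultravision facilitates the utilization of low impact laparoscopic surgery techniques whilst maintaining an adequate visual field throughout the procedure"; it adds that little CO₂ should need replacing. The research question in the Study Summary asks whether the device clears the visual field, "thereby facilitating low impact laparoscopic surgery when using a conventional insufflator"; section 2 repeats this with the verb *enabling*.

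Endpoint 1 is "The ability to complete the procedure without increasing pneumoperitoneum due to visualization". Objective 3 is different: completion at 10 mmHg or below. The Study Summary and section 25.2 plan descriptive statistics, and a comparison with earlier studies and literature to judge the results. Section 19 gives conversion to open surgery as an example of a reason for withdrawal at the investigator's discretion. Sections 11 and 19 have intraoperative exclusions withdrawn and replaced.

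**The concern.** A yes/no outcome does not remove the need for a comparison. *Enabled* says two things: the procedure was completed with the device, and it would have been less likely to be completed without it. The study observes only the first. The argument in section 25.1 is therefore invalid as written, and the hypothesis and research question carry the same claim.

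At stake is the conclusion of the study report. A high completion proportion would be reported as Ultravision having facilitated low impact surgery, when the data show that such surgery was feasible with Ultravision in use. A second, smaller matter affects the feasibility figure itself: if a converted case is withdrawn and then left out of the count, the proportion looks better than what happened.

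**Working it through.** **Inputs from the protocol.** n = 20, one arm (sections 7 and 25.1). Endpoint 1 is completed or not, with no threshold. Section 25.1 gives no reference rate, target rate, error level or power, so there is no sample size calculation to reproduce; 20 is asserted.

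**Step 1: is a no-device rate given anywhere?**
- The Study Summary and section 1 describe smoke build-up at low pressure with small ports, and say venting through 3 mm trocars works poorly. No completion or failure rate is attached.
- Section 1 summarises one randomized study (better visibility, shorter surgery) and a similar one at 10 mmHg with similar results. As summarised, neither is reported with a completion rate under 3 mm ports.
- The Study Summary and section 25.2 promise external comparison but name no dataset or completion rate.
- The Study Summary and section 1 say others have shown that operating under low impact conditions improves outcomes, so the protocol does not present such surgery as impossible without the device.

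The counterfactual is therefore neither observed nor cited.

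**Step 2: what would a perfect result say about the device?** Let p0 be the completion rate without the device. It is not in the protocol, so a range is assumed. If the device added nothing:

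P(20/20) = p0^20, and P(at least 19/20) = p0^20 + 20 × p0^19 × (1 − p0).

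| Assumed p0 | P(20/20) | P(≥19/20) |
|---|---|---|
| 0.70 | 0.0008 | 0.008 |
| 0.80 | 0.012 | 0.069 |
| 0.85 | 0.039 | 0.176 |
| 0.90 | 0.122 | 0.392 |
| 0.95 | 0.358 | 0.736 |
| 0.99 | 0.818 | 0.983 |

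The same 20/20 is strong evidence at p0 = 0.70 and unremarkable at p0 = 0.95. The protocol does not say which case applies.

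**Step 3: what 20 patients do give.** Exact (Clopper-Pearson) 95% limits. When all succeed, the lower limit is 0.025^(1/n); for 20/20, 0.025^(1/20) = 0.8316. Otherwise the lower limit is the 0.025 quantile of Beta(x, n − x + 1) and the upper limit the 0.975 quantile of Beta(x + 1, n − x).

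| Result | Proportion | 95% limits |
|---|---|---|
| 20/20 | 100% | 83.2% to 100% |
| 19/20 | 95% | 75.1% to 99.9% |
| 18/20 | 90% | 68.3% to 98.8% |

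These describe completion with the device in use and nothing else.

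**Step 4: effect of the denominator (illustrative counts, not forecasts).**
- Two conversions left out as withdrawals: 18/18 = 100%, lower limit 0.025^(1/18) = 81.5%. Counted as not completed: 18/20 = 90%, lower limit 68.3%.
- One conversion left out: 19/19 = 100%, lower limit 82.4%. Counted: 19/20 = 95%, lower limit 75.1%.

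**The case against.** The strongest reply is that this is a feasibility study and says so: in its title, in objective 1, and in the sentence of section 25.1 just before the one quoted. Its analysis is descriptive, a control may not be in patients' interest, and external comparison is planned. Endpoint 1 ties failure to visualization, the mechanism the device targets, and section 16 has the surgeon rate visualization and how often smoke was a problem.

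Much of this stands. One arm is a sound choice for feasibility, and the patient-interest reason for it is legitimate. But that reason explains the missing arm without supplying the missing rate. The surgeon's ratings bear on mechanism in each case, yet they too are made with the device in use. An external comparison could help only with a no-device completion rate under the same pressure and port conditions.

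Four stronger readings might be inferred, and the protocol does not support them:
- *That a control arm is required.* It is not, for the feasibility aim.
- *That the cited studies contain no usable rate.* Only the protocol's short summaries are at hand; all one can say is that the protocol reports none.
- *That conversions are removed from endpoint 1 by rule.* Withdrawal is discretionary, conversions are not on the list of replaced cases, and date, point and reason are recorded. The text leaves room for such cases to drop out; it does not order it. Nor are replaced intraoperative exclusions failures with the device in use: they are patients whose anatomy prevented its use.
- *That port changes go unrecorded.* Table 3 has no port item, but the case report forms are not shown, section 15 fixes the ports, and section 30.1 requires procedure reports and deviation forms to be kept.

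**Conclusion.** The inference in section 25.1 is wrong as written and should be fixed. The design supports a statement about feasibility of low impact surgery with Ultravision in use, with a lower limit of 83.2% at best. It does not support saying that the device enabled or facilitated the surgery, or measuring its relative impact. How far 20/20 would point to a device effect cannot be stated: over assumed no-device rates of 70% to 99%, its probability with no effect runs from 0.0008 to 0.82. This rests on the protocol alone; a separate analysis plan might name a comparator or an analysis set, but it would not repair the argument printed in section 25.1. The denominator point is a clarification whose size depends on how many conversions occur, which is unknown.

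**What to change.** 1. In section 25.1, delete the argument that the device enables or does not, so no control is needed, and the words on relative impact. Keep the feasibility aim and the patient-interest reason for one arm.
2. Reword the primary hypothesis and the research question (Study Summary and section 2) to feasibility of low impact surgery with Ultravision in use, keeping the visual-field and CO₂ elements as descriptive aims. Describe external comparisons as context, not as evidence that the device caused completion.
3. Replace the claim that 20 is enough to establish facilitation with the precision it gives: exact 95% lower limits of 83.2% (20/20), 75.1% (19/20) and 68.3% (18/20).
4. State that every procedure in which Ultravision was used stays in the endpoint 1 denominator, with conversion to open surgery counted as not completed as planned even if the patient is then withdrawn. Report replaced intraoperative exclusions separately.
5. Report two proportions: completion without a pressure increase due to visualization (endpoint 1) and completion at 10 mmHg or below throughout (objective 3). Sections 15 and 31 allow pressure to be raised for other reasons, so the two can differ. Describe any departure from the planned ports.

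Suggestions only: add a port item to Table 3, and reword the sentence "Success will be based on demonstration that the procedures using the Ultravision™ System achieves the following endpoints", since an item such as pain medication use has no target to achieve.

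Cost: protocol wording, one exact interval and one further proportion; no added patients or visits. The downside is a narrower claim and a completion proportion that may be lower.

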25.2. DATA ANALYSIS

Data collected will be summarized using descriptive statistics. Results from other studies conducted by Alesi as well as clinical data gleaned from the medical literature will be used to assess the relative significance of the study results. Additional exploratory analysis may be conducted during data analysis.

26. TRAINING PROCEDURES

The Principal Investigator in the study is a current Ultravision user, no additional device training is required. To ensure compliance with the study plan and regulatory requirements as well as accurate data collection, site training will include a detailed review of this Investigational Plan, case report form (CRF) completion instructions, adverse event reporting, device handling and inventory, monitoring logistics, and regulatory requirements.

27. ADMINISTRATION

This study is being conducted as an “Investigator Sponsored” post-market study. The Principal Investigator holds ultimate responsibility for the design, conduct, analysis, and reporting of the results from this study and is the primary contact for all matters related to this investigational plan. The Principal Investigator is also accountable for monitoring this investigation and performing those actions necessary to protect the scientific credibility of the way this study is conducted.

28. REGULATORY COMPLIANCE

The Principal Investigator is responsible for ensuring that the study is implemented at their site according to the Investigator Agreement, this protocol, applicable laws, regulations, and any conditions of approval by either the respective Institutional Review Board. The Principal Investigator is also responsible for ensuring that this study is conducted in a scientifically credible and ethical manner. The Principal Investigator is responsible for the selection, training, and supervision of site-specific research personnel. The Principal Investigator shall always perform responsibilities in a manner which protects the rights, safety, and well-being of subjects.

The Principal Investigator and all research staff participating in this investigation are expected to adhere to this investigational plan, Good Clinical Practices, applicable privacy laws, the Declaration of Helsinki, and any approval requirements imposed by an Institutional Review Board. The study will be submitted for review and approval by the Mercy Institutional Review Board.

28.1. INSTITUTIONAL REVIEW BOARD

Subjects may not be enrolled into this study until legal authority to do so has been granted by the authorizing Institutional Review Board. A copy of all approval letters must be maintained in the site file.

28.2. GOOD CLINICAL PRACTICES

The principles of Good Clinical Practices defined in ISO 14155:2011-1 Clinical investigation of medical devices for human subjects – Part 1: General Requirements, Part 2: Clinical investigation plans will be adhered to in the design, conduct, analysis, and reporting of results of this investigation.

29. PRIVACY AND CONFIDENTIALITY

30. THIS STUDY IS TO BE PERFORMED IN ACCORDANCE WITH ALL APPLICABLE PRIVACY LAWS. ALL DATA AND INFORMATION CONCERNING SUBJECTS AND THEIR PARTICIPATION IN THIS TRIAL ARE CONSIDERED CONFIDENTIAL. ONLY AUTHORIZED INVESTIGATORS AND APPROVED STUDY PERSONNEL WILL HAVE ACCESS TO SOME PORTIONS OF THESE CONFIDENTIAL FILES. INSTITUTIONAL REVIEW BOARDS AND OTHER REGULATORY AUTHORITIES ALSO HAVE THE RIGHT TO INSPECT AND COPY RECORDS PERTINENT TO THIS TRIAL. RECORDS AND REPORTS

The following records and reports must be created and/or maintained by the parties as specified below.

30.1. INVESTIGATOR RECORDS

Records to be maintained by the investigator in a designated study file include:

- Site information
 - Site signature log
 - Responsibility log
 - Training and credentials of study personnel
- Device information

- Ultravision and diathermy device inventory log including: date, quantity, lot numbers of all devices, identification of all persons the device was used on, and final disposition
 - Shipping documents
- Clinical study Plan/Protocol
 - Plan and all amendments
- Institutional Review Boards Records
 - Institutional Review Board Membership List
 - Submission to Institutional Review Boards
 - Approval letters
 - Notification of unanticipated adverse device events
 - updates/reports
 - Any other communication
- Screening and enrollment form
- Consent Form
 - Institutional Review Boards approved copy
 - Revised approved, consent forms
- Case Report Forms (CRFs)
 - Annotated CRF and/or CRF instructions (if applicable)
 - Blank CRFs and completion instructions (if applicable)
- Correspondence
 - All correspondence of material concern relating to the trial between the investigator and other parties (e.g. IRB).

The following records must be maintained for each subject enrolled in the trial:

- Signed Consent Form
- Completed CRFs
- Protocol Deviation Forms

- Complete medical records, including procedure reports, lab reports, professional notes, etc. for participating subjects.
- Records pertaining to subject death during the investigation (including death records, death certificate, and autopsy report, if performed)

